#### 3.1 Subject Selection

#### 3.1.1 Inclusion Criteria

Candidates for this study must meet ALL of the following criteria:

 Symptomatic paroxysmal AF who had at least one AF episode electrocardiographically documented within one (1) year prior to enrollment. Documentation may include electrocardiogram (ECG); Transtelephonic monitoring (TTM), Holter monitor or telemetry strip.

- 2. Failed at least one antiarrhythmic drug (AAD) (class I or III) as evidenced by recurrent symptomatic AF, or intolerable to the AAD.
- 3. Age 18 years or older.
- 4. Signed Patient Informed Consent Form (ICF).
- 5. Able and willing to comply with all pre-, post-, and follow-up testing and requirements.

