#### 5.15 Antiarrhythmic Drug (AAD) Management

#### 5.15.1 Definitions

• Antiarrhythmic drugs (AADs)

- The study protocol will classify and analyze the following:
  - Class I drugs (e.g., flecainide, propafenone, disopyramide, etc.)
  - Class III drugs (e.g., amiodarone, dronedarone, dofetilide, etc.)

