## • Previously Failed AAD

Any AAD that a subject has ever taken for the treatment of his/her AF, prior to enrollment, is considered a "previously failed AAD" if it meets both of the following conditions:

- prior to enrollment, the AAD was ineffective in controlling the subject's AF or produced intolerable side effects leading to its discontinuation;
- o the AAD is administered for AF
- New AAD

ANY AAD that was never taken for the treatment of AF prior to enrollment is considered a "new AAD" if the drug is administered to treat an "atrial tachyarrhythmia" post-enrollment.

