#### 7. ANALYSIS SETS

For the analysis of study endpoints, the analysis populations defined in the following will be used:

- Safety Population: The SP will consist of all enrolled subjects who have undergone insertion of the STSF/ST catheter and use of the VISITAG SURPOINTTM Module with EPU. The safety population (SP) will be used to analyze safety endpoints.
- Per Protocol (PP) Population: The PP population will include subjects who satisfy the following criteria. The PP population will be used for the analysis of effectiveness endpoints.
  - o are enrolled and meet all eligibility criteria
  - have undergone RF ablation
  - o are treated with the STSF/ST catheters with the VISITAG SURPOINT™ Module with EPU, and have been treated for the study-related arrhythmia

- Full Set Effectiveness Population: This population will include those who have met the following criteria. The full set effectiveness population will be used to analyze the effectiveness endpoints.
  - o are enrolled
  - o have undergone RF ablation
  - o are treated with the STSF/ST catheters with the VISITAG SURPOINT™ Module with EPU, and have been treated for the study-related arrhythmia

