#### 9.4.5 Subgroup Analyses

For the primary endpoints, subgroup analysis will be performed for the following subgroups after the 12 months follow-up is complete.

PP population will be used for primary effectiveness endpoint and safety population will be used for primary safety endpoint. The number and percentage of subjects with the primary effectiveness and safety endpoints will be presented in each subgroup. Exact 95% confidence intervals will be constructed around the percentages in each subgroup. Fisher's exact test will be used to test for statistical difference between the subgroups at the 5% significance level. Fisher-Freeman-Halton Exact Test will be used when the number of subgroup is greater than two. Since subgroup analyses are unadjusted, any differences especially in subgroups defined based on post-baseline characteristics, may be confounded by differences in baseline characteristics. For e.g., repeat procedure vs. no repeat procedure during the blanking period – patients with more advanced disease at baseline may require a repeat procedure impacting the observed safety and effectiveness rates.

- Age group: <60 vs. >=60 years
- Previously failed AAD Class I&III vs Class II&IV
- Repeat procedure during blanking period: Repeat procedure conducted vs. Not conducted
- Operator's ablation procedure experience level: More experienced (≥ 75 left atrial ablation procedures for atrial fibrillation in the past 12 months) vs. Less experienced (< 75 left atrial ablation procedures for atrial fibrillation in the past 12 months)
- Segments of Tag Index values: above or below or at target Biosense Webster, Inc

- Contact Force: <=10, 11-15, 16-20 and >20 grams
- Ablation targets

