#### 9.4.6 Additional Analysis for Primary Effectiveness Endpoint

Univariate and multivariate logistic regression models will be used to examine the impact of the covariates on the primary effectiveness endpoint. If the sites are not poolable, then study site and operators will be treated as random effects in the regression model. All covariates included in the analysis will consist of the following:

	Definition/ Variables	Note
Demographics	
 
Age
 
Gender
 
Ethnicity
 
Race
 
Study Site
 
	
 
Continuous variable (unit: year)
 
Male, Female
 
Hispanic/ Latino or not
 
Asian, Black, Caucasian, Other
 
Random Effect if sites not poolable
 

Medical History	
 
Diabetes
 
Hypertension
 
Structural heart disease
 
Atrial Flutter
 
Duration of AF history
 
Frequency of AF episodes
 
	
Cardiac Medical History	
 
Previously tried Class I AADs
 
Previously tried Class II AADs
 
Previously tried Class III AADs
 
Previously tried Class IV AADs
 
	
 
Class I: Disopyramide, Flecainide, Propafenone, Quinidine
 
Class II: (Beta-Blocker): Acebutolol, Atenolol, Metoprolol, Propranolol, Sotalol, and other Beta-Blocker
 
Class III: Amiodarone, Dofetilide
 
Class IV: Verapamil, Diltiazem
 

TTE Result	Baseline left atrial dimension	
Ablation Procedure	
 
Repeated ablation procedure or not
 
Procedure success
 
Use of Isoproterenol
 
Use of Adenosine
 
Agilis Sheath
 
Other Sheath
 
Total procedure time
 
CF values
 
Average power
 
Average impedance
 
Average temperature
 
Total RF ablation time
 
Tag index value
 
Etc.
 
	

The primary effectiveness endpoint will be the dependent variables and the covariates will be treated as independent variables. Univariate logistic regression models will be conducted for each of the potential predictors. A p-value <0.20 is to be used as the cut-off point for screening covariates. Forward model selection will be used to select predictors that remain significant at p-

value <0.05 in the multivariate model. Interaction terms may be examined based on those covariates that remain significant in the final model.

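### The AAD-class subgroup in SAP 9.4.5 does not define two separable groups among eligible subjects, and the SAP and protocol drug-class lists disagree

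*SAP*

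**What the plan says.** **The subgroup.** SAP 9.4.5 lists "Previously failed AAD Class I&III vs Class II&IV" among its subgroups for the two primary endpoints. Effectiveness is examined in the PP population and safety in the safety population. Each level gets an exact 95% confidence interval, and two levels are compared by Fisher's exact test at 5%. The section does not say whether the levels exclude each other, or where a subject who failed drugs of both kinds belongs.

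**Eligibility.** Criterion 2 in Protocol 3.1.1 reads "Failed at least one antiarrhythmic drug (AAD) (class I or III) as evidenced by recurrent symptomatic AF, or intolerable to the AAD". The definition of a previously failed AAD in Protocol 5.15.1 also counts a drug that "produced intolerable side effects leading to its discontinuation".

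**Populations.** SAP 7 admits to the PP population only subjects who "are enrolled and meet all eligibility criteria". The safety population has no eligibility condition: it needs enrolment, catheter insertion and use of the module.

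**Drug classes.** Protocol 5.15.1 lists Class I and Class III drugs, the latter as "Class III drugs (e.g., amiodarone, dronedarone, dofetilide, etc.)", an open list. SAP 9.4.6, the only place where the SAP assigns drugs to classes, has "Class III: Amiodarone, Dofetilide" with no open end, and places sotalol among the beta-blockers in Class II.

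**The concern.** A two-group comparison needs each subject in one group only, and both groups must be able to contain subjects. Here the entry criterion puts every PP subject on the first side of the contrast, so the second side has no members of its own. Whoever programs the analysis must choose a meaning for it after 12-month data exist, in a study whose sponsor is not blinded to individual or aggregated data (Protocol 7.3, SAP 3).

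The class lists add a second difficulty. SAP 9.4.5 has no drug list of its own, so coding would naturally follow SAP 9.4.6. A subject could then be eligible on one classification and analysed on another, and the second group could be filled by a coding difference instead of a real difference in drug history.

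At stake is one pre-specified exploratory comparison and the coding of the AAD covariates.

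**Working it through.** The plan gives no figure for this subgroup, so there is none to reproduce. The check is mainly one of logic.

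**Size of the PP population.** SAP 8 gives 330 enrolled, 10-15% attrition, and about 30 subjects lost before treatment.
- 330 × 0.85 = 280.5 and 330 × 0.90 = 297
- 330 − 30 = 300

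So N is about 280 to 300.

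**Readings of the contrast**, assuming classes are coded the same way for eligibility and analysis:

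| Meaning of the second side | PP population (effectiveness) | Safety population |
|---|---|---|
| Failed Class II/IV drugs only | 0 subjects, because criterion 2 puts everyone on the first side | Only treated subjects who did not meet criterion 2 |
| Failed any Class II/IV drug | A subset of the first side. If m subjects qualify, the table has N + m entries from N subjects | Same overlap for all eligible subjects |

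Reading Class I&III as failure of both classes does not help. Subjects who failed only one of them have no cell, and a Class II/IV-only group is still empty in PP.

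**Fisher's test with an empty side.** Take N = 300 and the planning success rate of 65%, so 300 × 0.65 = 195 successes and 105 failures on the first side, and 0 and 0 on the second. The margins allow only one table, so p = 1.0 whatever the data. No interval can be formed for the empty side.

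**Fisher's test with a handful of subjects.** Suppose k PP subjects reach the second side through class coding (k is an assumption; the documents give no number). The remaining 300 − k have 65% success, rounded to whole subjects. If all k fail, the probability of that table is C(F, k) / C(300, k), with F the total failures. This is also the two-sided p here, because every other table is more probable.
- k = 1: F = 106, p = 106/300 = 0.35
- k = 2: F = 106, p = (106 × 105)/(300 × 299) = 0.12
- k = 3: F = 107, p = (107 × 106 × 105)/(300 × 299 × 298) = 0.045

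With one or two subjects the test cannot reach 5% even when all of them fail. With k = 5 and 3 successes, the exact 95% interval runs from about 15% to 95%.

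**Class lists side by side.**

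| Drug | Protocol 5.15.1 | SAP 9.4.6 |
|---|---|---|
| Dronedarone | Named in Class III | Not listed in any class |
| Sotalol | Not named; the Class III list is open-ended | Named in Class II |

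A subject whose qualifying failure was dronedarone has no class under the SAP list. If a site accepted failed sotalol as Class III for eligibility (an assumption; the documents do not say), the SAP would code that subject as Class II.

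**The case against.** The best defence is that the bullet lacks only an allocation rule. If each subject is counted once, as failed Class I/III only against failed Class I/III plus Class II/IV, the groups are disjoint, the second can have members, and Fisher's test applies. That is correct, and it is one of the remedies below. It is not, however, the contrast the bullet states, so the bullet has to be changed.

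Four stronger conclusions that a reader might draw do not stand:

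- **One side is empty for both endpoints.** Emptiness follows only in PP, only for a Class II/IV-only group, and only with consistent coding. The safety population is not limited to eligible subjects, and SAP 9.4.4.3 foresees treated subjects later found ineligible. Still, a safety comparison of criterion 2 violators with everyone else would say little about drug history.
- **No valid test by Class II/IV history is possible.** The single-count split just described shows otherwise.
- **The study analyses only Class I and III drugs.** Protocol 5.15.1 introduces those two classes with "The study protocol will classify and analyze the following", but SAP 9.4.6 expressly plans Class II and IV history as covariates.
- **The question of drug history goes unanswered.** For effectiveness, SAP 9.4.6 models previously tried Class I, II, III and IV drugs separately in the PP population. Those covariates record drugs tried, not failed, and there is no counterpart for safety, so a narrower gap remains.

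It is also fair to say that this is one of seven unadjusted subgroups, that the SAP itself warns of confounding in them, and that no success criterion depends on it.

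**Conclusion.** The point holds. As written, the subgroup gives no valid two-group comparison in the PP population: the second side has 0 of about 280 to 300 subjects if it means Class II/IV only, and lies wholly inside the first side if it means any failed Class II/IV drug. This rests on criterion 2 being enforced for PP membership and on the same class coding being used for eligibility and analysis. The second assumption is not secure, because the two lists treat dronedarone and sotalol differently. In the safety population, a Class II/IV-only group is not forced to be empty but could consist only of treated subjects who did not meet criterion 2.

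The consequence is small. It reaches an exploratory subgroup and the AAD covariates in SAP 9.4.6. The primary analyses, the success rules, error control and power are unaffected. It is worth correcting because the change is cheap and removes a choice that would otherwise be made with outcome data in hand.

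**What to change.** 1. Replace the bullet in SAP 9.4.5 with mutually exclusive levels that can occur among eligible subjects, counting each subject once. Two options:
   - failed Class I only, Class III only, or both (three levels, for which SAP 9.4.5 already names the Fisher-Freeman-Halton test); or
   - if Class II/IV history is the question, failed Class I/III only against failed Class I/III plus Class II/IV.
2. State how the safety analysis handles treated subjects who did not meet criterion 2, for example by listing them separately.
3. Adopt one closed drug-class list, the same in Protocol 5.15.1 and in SAP 9.4.5 and 9.4.6, that explicitly assigns dronedarone and sotalol. Pointing to Protocol 5.15.1 as it stands is not enough: its lists are open-ended examples and it has none for Class II or IV.

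The cost is one SAP bullet, one sentence on the safety population and one aligned list. Protocol 5.3 already collects failed AADs at baseline. If the second option is chosen, confirm that the case report form records failure, and not only use, of Class II and IV drugs.

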#### 4.1.2 Primary Safety Endpoint

The primary safety endpoint is the incidence of any primary adverse event occurring within 7 days following an AF ablation procedure (including the initial and repeat procedures) using the STSF/ST catheter with the EPU per protocol, except atrio-esophageal fistula and PV stenosis, which may also be considered as primary adverse events if occurring greater than seven (7) days post the ablation procedure .

Primary adverse events include the following conditions (refer to Table 6-1 Primary Adverse Events for detailed instructions for defining these adverse events):

- Death
- Atrio-esophageal fistula
- Cardiac Tamponade\*+/Perforation+
- Myocardial infarction (MI)
- Stroke / Cerebrovascular accident (CVA)†, ††
- Thromboembolism
- Transient Ischemic Attack
- Diaphragmatic paralysis

- Pneumothorax
- Heart block
- PV stenosis
- Pulmonary edema (Respiratory Insuffciency)
- Vagal Nerve Injury
- Pericarditis
- Major vascular access complication / bleeding
- \* Hemodynamic compromise or instability is defined as Systolic BP < 80 mm Hg.
- + Cardiac Tamponade/Perforation occurring within 30 days of the AF ablation process will be considered Primary AEs
- † Subjects with non-focal global encephalopathy will not be reported as a stroke without unequivocal evidence based upon neuroimaging studies.
- †† Modified Rankin score assessments should be made by certified individuals.

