#### **5.1.2** Primary Safety Endpoint

The primary safety endpoint is the proportion of subjects with any primary adverse event (PAE) occurring within 7 days following an AF ablation procedure (including the initial and repeat procedures) using the STSF/ST catheter with EPU, except atrio-esophageal fistula and PV stenosis , which may also be considered as primary adverse events if occurring greater than 7 days post the ablation procedure. The PAE rate will be compared against the performance goal of 14%.

The final analyses for primary safety endpoint will apply Bayesian methods and use a beta-binomial model .

The hypotheses to be tested for this evaluation are:

$$H_0: q \ge 0.14$$
 vs.  $H_A: q < 0.14$ 

where q is the PAE rate.

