#### 8. SAMPLE SIZE JUSTIFICATION

The final analyses for primary safety and effectiveness endpoints will apply Bayesian methods and use a beta-binomial model .

The power calculations for the Bayesian adaptive design are presented in the simulation report Appendix B Table 6 (probability of success). Under the assumption of 65% success rate for primary effectiveness and 8% rate for primary safety, with 330 subjects, assuming 10-15% attrition rate, we will have more than 90% power for declaring success for each of the primary endpoints controlling the type-I error at 5%.

The total of 330 enrolled subjects includes 280 subjects who will be treated using STSF catheter with EPU and 50 subjects be treated using ST catheter with EPU. Approximately 30 subjects may be excluded or discontinued before receiving treatment assuming 10-15% attrition rate.

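### The safety comparison of subjects with and without a blanking-period repeat ablation gives the groups unequal at-risk windows, and the SAP's caveat does not mention this

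*SAP*

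**What the plan says.** SAP 5.1.2 defines the primary safety endpoint as a proportion of subjects and counts any PAE "occurring within 7 days following an AF ablation procedure (including the initial and repeat procedures) using the STSF/ST catheter with EPU". Not every window is 7 days. Protocol 4.1.2 adds that "Cardiac Tamponade/Perforation occurring within 30 days of the AF ablation process will be considered Primary AEs", and atrio-esophageal fistula and PV stenosis may count later.

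SAP 9.4.5 analyses both primary endpoints by subgroup, safety in the safety population. It presents raw percentages with exact 95% intervals and tests for a difference with Fisher's exact test at the 5% level. One listed factor is "Repeat procedure during blanking period: Repeat procedure conducted vs. Not conducted".

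The same section warns that unadjusted subgroups may be confounded, above all those formed after baseline. It takes this factor as its example: "patients with more advanced disease at baseline may require a repeat procedure impacting the observed safety and effectiveness rates". It gives no other reason for caution. Neither document plans a per-procedure PAE rate for this subgroup.

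**The concern.** The grouping variable also creates exposure. Having a repeat ablation with the study system puts a subject in the repeat group and opens a further window in which that subject can become a PAE case. The subject-level rates can therefore differ when every procedure carries the same risk.

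This is a different mechanism from the one the SAP names. It would remain if the two groups were identical at baseline, and baseline adjustment would not remove it. A reader who follows the caveat would put a higher rate in the repeat group down to more advanced disease, or take it as evidence that repeat ablation is more hazardous. The table cannot tell these explanations apart because it never separates index events from repeat events. At stake is how a labelled 5% safety test in the final report is read.

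**Working it through.** **Inputs.** SAP section 8 gives the planning values: "Under the assumption of 65% success rate for primary effectiveness and 8% rate for primary safety, with 330 subjects, assuming 10-15% attrition rate". Treated numbers are then 330 × 0.90 = 297 down to 330 × 0.85 = 280.5. The documents do not give the share of subjects with a blanking-period repeat, the relative risk of a second procedure, or how an index PAE affects the chance of a repeat. These are assumptions below, shown as ranges.

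**The plan's own figure.** The final safety rule (Beta(1,1) prior, posterior probability of a rate below 14% greater than 0.95) allows at most 31 PAEs at n = 297. At a true rate of 8% the power is 94.6%, and at n = 281 it is 93.4%, ignoring the interim looks. The stated power above 90% is reproduced.

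**Equal, independent risk q per procedure, no selection.** One window gives q. Two windows give 1 − (1 − q)². At q = 8% this is 1 − 0.92² = 15.4%, a ratio of 1.92. At q = 2% the ratio is 1.98, and at q = 14% it is 1.86.

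**Departures, each from the q = 8% case.**
- Second-procedure risk half the index risk: 1 − 0.92 × 0.96 = 11.7%, ratio 1.46. At a quarter: 1 − 0.92 × 0.98 = 9.8%, ratio 1.23. At 1.5 times: 1 − 0.92 × 0.88 = 19.0%, ratio 2.38.
- A share g of the no-repeat group is re-ablated on Days 91-365, which also opens a window. The comparator rate is (1 − g) × 8% + g × 15.36%. For g = 5% to 20% this is 8.4% to 9.5%, ratio 1.84 to 1.62.
- Subjects with an index PAE are s times as likely to be re-ablated, with a 5% repeat share. The ratio is 1.44 at s = 0.5, 1.20 at s = 0.25 and 0.95 at s = 0. In the last case the repeat group has 8% from its second window alone, and the comparator has 0.08/0.95 = 8.4%. At a 15% repeat share the same extreme gives 0.08/(0.08/0.85) = 0.85.

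**Fisher's test**, two-sided 5%, exact enumeration, n = 297:

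| Repeat subjects (assumed) | 15 | 30 | 45 |
|---|---|---|---|
| 15.4% vs 8.0% | 16.5% | 26.5% | 30.8% |
| 11.7% vs 8.0% (half second-procedure risk) | about 8% | about 11% | about 12% |
| 8.0% vs 8.0% | 2.4% | 2.9% | 3.2% |

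With a repeat share of only 2% (6 of 300), rejection is 6.7% in the equal-risk case, against 1.5% with equal rates.

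**Reading 8% as the plan does.** The planned 8% is a per-subject rate that already includes repeats. Solving q + f·q(1 − q) = 0.08 for a repeat share f of 5%, 10% and 15% gives q = 7.6%, 7.3% and 7.0%. The two-window rates are then 14.7%, 14.1% and 13.5%. The ratio stays at 1.92-1.93.

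**The case against.** The strongest reply is that SAP 9.4.5 already singles out this subgroup as not comparable and names safety in doing so, and that the analysis feeds no decision. Both are true. They limit the severity, but the caveat still gives a reason that is not the structural one.

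Three stronger readings are tempting, and the documents do not support them.

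- A reader might infer that the PAE rate must nearly double. That needs equal and independent risk per procedure, no selection on the index outcome, a study-system repeat in every repeat subject, and no later repeats in the comparator. The documents state none of these. Protocol 5.18 leaves repeats to the physician's discretion, only repeats with the study system open a window, and evaluation-period repeats fall in the no-repeat group.
- A reader might infer that the repeat group should be expected to exceed the 14% performance goal. Once 8% is taken as the per-subject rate, the figure is marginal at a 10% repeat share and below 14% at 15%. In any case the SAP compares no subgroup with 14%.
- A reader might say that Fisher's test fails to hold its level. Strictly, if the subject-level proportions really are 15.4% and 8.0%, rejecting is a correct detection. What fails is the interpretation of that difference as one of risk per procedure or of patient severity.

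**Conclusion.** The concern holds as a matter of unequal exposure. The planned safety comparison gives subjects with a study-system repeat at least one extra at-risk window, and the SAP does not say so. The artefact can approach a doubling (ratio 1.92, Fisher rejection about 16-31% with 15-45 repeat subjects among 297) under equal, independent risk and no selection. Plausible departures give ratios of about 0.95 to 1.9: lower still if index-PAE subjects are never re-ablated and repeats are common, higher if repeats are riskier. At half the second-procedure risk, rejection is about 8-12%. Selection can also hide a real excess, so the same table may show a false signal or mask a true one. The repeat share, relative risk and selection factors are assumptions. The primary success rule and its stated power are not affected, and the severity is minor.

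**What to change.** In SAP 9.4.5, for the safety endpoint only, replace the repeat versus no-repeat Fisher test with a per-procedure table:

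- PAEs in the window of the index procedure, over all safety-population subjects.
- PAEs in the window of a repeat procedure, over all repeat procedures done with the study system.

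Give each rate an exact 95% interval. Use the event-specific windows: 7 days in general, 30 days for tamponade/perforation, and the later window for fistula and PV stenosis. SAP 5.1.2 sets no upper limit for that last window and SAP 9.4 says 3 months, so the table should state which applies. Add a sentence to the caveat that subjects with a repeat have additional at-risk windows.

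Do not substitute a comparison of index-procedure PAEs by later repeat status. It equalises the windows but conditions on an event after the index procedure. If index-PAE subjects are half as likely to be re-ablated, the repeat group's index rate is 0.04/(0.04 + 0.92) = 4.2%, against 8.2-8.7% in the others for repeat shares of 5-15%, with no true difference.

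The cost is one or two SAP sentences and one table from event and procedure dates that the study needs anyway. The plan must also say to which procedure an event is assigned when the longer windows of two procedures overlap.

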#### 5.7 Contact Force (CF) Settings

Operators should select individualized CF target ranges based on their case experience and the prior results from the THERMOCOOL SMARTTOUCH® SF catheter IDE trial.

- Contact Force settings:
  - Contact Force Target range: 5-25 gram (recommended)
  - Minimum CF of 3-5 grams
- Risk of cardiac tamponade and perforation may correlate with higher CF ( $\geq$  40 g) used during RF ablation.
  - For  $CF \ge 20g$ , power should be  $\le 35$  watts.
- Contact force data and individual procedure working ranges will be collected for each RF application during a study ablation procedure for offline analysis.

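### Safety has no ordered or continuous contact-force analysis: the only planned test compares four ordered bands as if they had no order

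*SAP*

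**What the plan says.** SAP 9.4.5 lists "Contact Force: <=10, 11-15, 16-20 and >20 grams" among the subgroups for the primary endpoints. For the PAE analysis, "safety population will be used for primary safety endpoint". Each band gets a count, a percentage and an exact 95% interval. On testing, "Fisher's exact test will be used to test for statistical difference between the subgroups at the 5% significance level", and "Fisher-Freeman-Halton Exact Test will be used when the number of subgroup is greater than two". No trend test is named. The section warns that these comparisons are unadjusted and that post-baseline subgroups may be confounded.

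SAP 9.4.6 lists contact-force values as a covariate in logistic regression, without banding them, but for one outcome only: "The primary effectiveness endpoint will be the dependent variables and the covariates will be treated as independent variables". SAP 5.3 and Protocol 4.3 and 7.5.3 treat contact force as descriptive procedural data.

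The protocol raises a possible link with harm in two places. Section 1.1 cites ex vivo evidence that higher force may lead to more serious adverse events. Section 5.7 says "Risk of cardiac tamponade and perforation may correlate with higher CF", and attaches a value of at least 40 g. Section 5.7 also has contact force recorded for every RF application.

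**The concern.** Contact force is a continuous measurement, and its bands have a natural order. An omnibus test over four bands spreads its power over every kind of difference, including patterns nobody would expect. For effectiveness this matters little, because SAP 9.4.6 also uses the values in a regression. For safety, where the protocol voices its caution about force, the unordered test is the only planned comparison. With few events, a moderate rise across the bands could be reported as no difference between contact-force groups.

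Two smaller gaps sit beside this. Whole-number band edges leave a value such as 10.5 g in no band unless values are rounded, and no rounding rule is given. SAP 9.4.5 also does not say how many readings per procedure become one value per subject.

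**Working it through.** **Inputs from the documents.** SAP 8: "Under the assumption of 65% success rate for primary effectiveness and 8% rate for primary safety, with 330 subjects, assuming 10-15% attrition rate"; also "Approximately 30 subjects may be excluded or discontinued before receiving treatment assuming 10-15% attrition rate". Treated subjects are about 330 − 30 = 300; applying 10–15% to 330 gives about 280 to 297. Expected PAEs are 300 × 0.08 = 24 (about 22 to 24 for 280 to 297). The subgroup level is 5%.

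**The plan's own figure.** The plan states no power for the contact-force comparison. It does state more than 90% for each primary endpoint. Under SAP 9.4.1, safety succeeds if Pr(q < 0.14) > 0.95 under Beta(1 + y, 1 + n − y). Without interims, n = 300 requires y ≤ 31. Then P(Y ≤ 31 | 300, 0.08) = 94.0%, with type I error 3.6% at q = 0.14. For n = 280 (y ≤ 29), 297 (y ≤ 31) and 330 (y ≤ 35), power is 93.7%, 94.6% and 96.3%. The statement reproduces for safety, and the 8% and 300 are a fair basis for what follows.

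**Assumptions not in the documents.** These are the band shares and the gradient. Steady gradient: logit(p_k) = a + k·log(OR) for k = 0 to 3, with a set so that the overall rate is 8%. With equal bands and OR 1.5, the band rates are 4.2, 6.1, 8.9 and 12.8%.

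**Method.** All 2×4 tables were enumerated given their margins. The Fisher-Freeman-Halton p-value sums the probabilities of all tables no more likely than the observed one. The exact Cochran-Armitage p-value (two-sided) uses T = Σ k·y_k and its distance from expectation. Power at 5% is then averaged over the number of events.

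**Steady gradient: power %, Fisher-Freeman-Halton / exact trend (difference)**

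| Band sizes | OR 1.25 | 1.5 | 1.75 | 2.0 | 2.5 |
|---|---|---|---|---|---|
| 75 each | 13.3 / 18.5 (+5) | 36.4 / 50.4 (+14) | 62.2 / 76.9 (+15) | 80.4 / 90.7 (+10) | 95.5 / 98.6 (+3) |
| 60/120/90/30 | 12.2 / 14.5 (+2) | 29.6 / 38.4 (+9) | 51.4 / 63.3 (+12) | 70.2 / 80.9 (+11) | 90.9 / 95.7 (+5) |
| 45/135/90/30 | 11.3 / 13.5 (+2) | 26.9 / 35.4 (+8) | 47.2 / 59.2 (+12) | 65.8 / 77.3 (+11) | 88.3 / 94.2 (+6) |
| 30/120/105/45 | 9.5 / 13.4 (+4) | 23.1 / 35.0 (+12) | 42.0 / 58.6 (+17) | 60.3 / 76.5 (+16) | 84.6 / 93.6 (+9) |
| 90/120/60/30 | 14.7 / 17.0 (+2) | 37.0 / 45.2 (+8) | 62.2 / 71.8 (+10) | 80.7 / 87.8 (+7) | 96.1 / 98.2 (+2) |

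With no effect, rejection is about 5% for Fisher-Freeman-Halton and about 4% for the trend test, so the gain is not bought with type I error.

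**Continuous force.** A 2,000-run simulation assumed force normal with mean 14 g and SD 4.5 g, and used an ordinary one-covariate logistic likelihood-ratio test. At odds ratios per SD of 1.4, 1.6, 1.8 and 2.0, Fisher-Freeman-Halton had 23, 42, 57 and 75% power and the regression 35, 57, 76 and 88%. The gain is 12 to 19 points.

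**Rise only above 20 g.** The rate in the lower three bands is p0 = 24 / (n1 + n2 + n3 + RR·n4). For 60/120/90/30 and RR 3, p0 = 24 / (270 + 90) = 6.7%, against 20% in the top band.

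| Band sizes | RR 2 | RR 3 | RR 4 |
|---|---|---|---|
| 75 each | +1 | −1 | −2 |
| 60/120/90/30 | −6 | −13 (48.6 / 35.6) | −16 |
| 45/135/90/30 | −5 | −12 | −15 |
| 30/120/105/45 | −3 | −8 | −8 |

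**Gradient only in tamponade.** Protocol 1.3.1 reports 4/161 = 2.5% and 2/159 = 1.3%, or 31% and 16% of an 8% PAE rate. The gradient was placed on that component alone, with band sizes of 75 each, 45/105/105/45 and 30/150/90/30. At OR 1.5 to 2.0 per band, exact power is at most about 12% (Fisher-Freeman-Halton) and 17% (trend), a difference of about −1 to +4 points. Neither test is informative there.

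**The case against.** The strongest objection is that the protocol does not predict a steady rise from the lowest band to the highest. Section 1.1 is hedged and ex vivo. Section 5.7 is hedged too, and ties the risk to 40 g or more, which lies above its recommended 5–25 g range and inside the top band. For a rise confined to the top band, the planned test is level with a trend test or better. The PAE composite also includes events such as access-site bleeding and pneumothorax, for which no link with force is stated; these would flatten any gradient. Finally, the banded percentages and intervals would show a rise whatever the p-value, and a sharper p-value on a post-baseline measurement would still be confounded.

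Most of this stands. It rules out two stronger readings that a reader might infer. One is that the SAP discards a fixed 10 to 15 points of power against a gradient that the protocol expects: the text says only that risk may rise, and that loss follows only from moderate assumed gradients. The other is that a trend test should replace Fisher-Freeman-Halton: under a threshold pattern the replacement could lose power.

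What the objection does not remove is the asymmetry. Effectiveness gets a regression on contact force and safety does not, although the data are collected and safety is where the protocol raises the question.

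**Conclusion.** The point holds as a modest improvement to an exploratory analysis. No planned test or model of the primary safety endpoint uses the order or scale of contact force. The cost is about 2 to 17 points of power, assuming a steady gradient of OR 1.25 to 2.5 per band, about 24 PAEs in 300 subjects and the five band splits shown. It is nil, or reversed by up to about 16 points, if risk rises only above 20 g. It is small if only tamponade responds to force. The documents do not say which pattern to expect, which is a reason to have both kinds of analysis.

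A reader might also infer that the primary safety conclusion is at risk. It is not: the success rule in SAP 9.4.1 does not use this comparison.

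**What to change.** In SAP 9.4.5:

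- Keep the banded counts, percentages, exact intervals and the Fisher-Freeman-Halton test.
- For the primary safety endpoint, add a one-covariate Firth or exact logistic regression on the subject's contact force as a continuous variable, an exact Cochran-Armitage trend test over the four bands, or both. Fix the choice in advance and label it exploratory and unadjusted. About 24 events support little more than one covariate.
- State how the per-application readings become one value per subject (for example, the mean over RF applications), and use the same summary for the bands.
- Make the bands contiguous: ≤10, >10–15, >15–20 and >20 g.

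The cost is a few lines of SAP text and code, with no new data. The downside is at least one more exploratory p-value, and low power of the added analysis against a threshold or non-monotone pattern. That is why Fisher-Freeman-Halton should stay.
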